This will be a phase II randomized clinical trial of patients with histologic documentation of metastatic colorectal cancer, who have received local and currently approved standard therapies, excluding RGF. Patients will be randomized 1:1 to RGF or VOR/HCQ (see schema below) and stratified by KRAS status (wild-type or mutated). We will give VOR 400 mg PO daily and HCQ 600 mg PO daily in 4-week cycles. Patients will require imaging up to 6 weeks prior to enrollment and will be assessed for measureable evidence of mCRC. Crossover to the other arm will be allowed, but OPTIONAL, and will be determined by the treating physician for the patient's best interest.

5.1 Sample size:

Historically, the mPFS for previously treated mCRC patients treated with RGF is 1.9 mos. We predict VOR/HCQ will improve mPFS to 3.8 months. We expect 5% lost to follow-up. Assuming a 36-month accrual period with 1 year for follow up, 36 subjects per group are necessary to obtain 80% power. With 5% lost to follow-up the sample size required per group is 38 ($=36/0.95$), therefore, the total required sample size is 76 subjects. As a result, the target accrual rate is 2-4 patients/month to achieve a target accrual at 36 months with an additional 12month follow-up.

5.2 Study Schema:

*** Crossover to the other arm will be allowed, but OPTIONAL, and will be determined by the treating physician for the patient's best interest.

Randomization:

Randomization list will be sent to pharmacy. Once the patient is registered onto the study, the pharmacist will assign the patient to one of the treatment arms. The patient should start the treatment within 14 days of randomization.

Upon randomization, regorafenib prescription will be sent to specialty pharmacy. If the patient receives the medication in <14 days, then the patient can start at home. The start date will be C1D1. If the patient receives ≥ 14 days, then the patient will need a C1D1 clinical visit and labs: CBC, CMP, CEA and biomarkers.

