Hepatic: AST increased (58% to 65%; grade 3: 3% to 5%; grade 4: 1%), ALT increased (39% to 45%; grade 3: 4% to 5%; grade 4: 1%), hyperbilirubinemia (33% to 45%)

Neuromuscular & skeletal: Stiffness (14%)

Renal: Proteinuria (33% to 60%; grade 3: 3%)

Miscellaneous: Infection (31% to 32%; grade ≥ 3 : 5% to 9%) 1%
to 10%:

Cardiovascular: Myocardial ischemia and infarction (1%)

Gastrointestinal: Taste disturbance (8%), xerostomia (5%), gastroesophageal reflux (1%)

Neuromuscular & skeletal: Tremor (2%)

Respiratory: Dyspnea (2%)

<1% (Limited to important or life-threatening): Bradycardia, erythema multiforme, gastrointestinal fistula, hypertensive crisis, liver injury (severe), liver failure, reversible posterior encephalopathy syndrome (RPLS), skin cancer (keratoacanthoma, squamous cell carcinoma), Stevens-Johnson syndrome, toxic epidermal necrolysis

Pregnancy Category D:

Risk Summary Based on its mechanism of action, Regorafenib can cause fetal harm when administered to a pregnant woman. There are no adequate and well-controlled studies with Regorafenib in pregnant women. Regorafenib was embryo lethal and teratogenic in rats and rabbits at exposures lower than human exposures at the recommended dose, with increased incidences of cardiovascular, genitourinary, and skeletal malformations. If this drug is used during pregnancy or if the patient becomes pregnant while taking this drug, the patient should be apprised of the potential hazard to a fetus

5.7 Primary and Secondary Endpoints: Primary endpoint:

- PFS-1: measured from the start of the first treatment the patient is randomized to until the date the criteria for progression are met or the date the patient is taken off study for any reason, whichever is shorter.

Secondary endpoints:

- OS: measured from the start of treatment on trial until the death of the patient.

- mPFS-2: measured from the start of the crossover treatment (OPTIONAL, second regimen) until the date the criteria for progression are met or the date the patient is taken off study for any reason, whichever is shorter.
- Response: measured as best response, complete response (CR) or partial response (PR), as defined by Response Evaluation Criteria in Solid Tumors (RECIST 1.1) Committee.
- Adverse events: grade 1-5 adverse events according to the National Cancer Institute Common Terminology Criteria for Adverse Events (NCI-CTCAE) v4.0; measured at baseline, each cycle, and at off study date.

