For Cycle 1, for patients who are assigned to VOR/HCQ arm, if baseline labs were done <14 days from C1D1, then can omit CBC, CMP, CEA and LDH. Upon randomization, regorafenib prescription will be sent to specialty pharmacy. If the patient receives the medication in <14

days, then the patient can start at home. This start date will be C1D1. If the patient receives ≥ 14 days, then the patient will need a C1D1 clinical visit and labs: CBC, CMP, CEA, LDH.

Repeat EKG after cycle 2 only if clinically relevant

Ω For Cycle 1 Day 15 and Cycle 2 Day 15, we will check CBC and CMP to evaluate for toxicity. Specifically, for RGF, we will monitor ALT, AST and bilirubin. For VOR, we will monitor blood counts. History and physical exam only as needed or if clinically indicated.

± Baseline CT should be Day -36 to Day -1. Every other cycle CT scans can be done +/- 4 days. Off treatment CT scan is done if not done at disease progression or in the last 28 days. (See Appendix 13.1 for definitions of response).

* ONLY required for patients receiving HCQ on study: If the patient is randomized to VOR/HCQ arm, and the patient is 70 year or older or has baseline ophthalmologic pathology (i.e., diabetic retinopathy), then a comprehensive eye exam will be done at baseline. If the

patient continues to receive HCQ on study at 6 months, a repeat comprehensive eye exam will be done at 6 months and then every 6 months while receiving HCQ on study. If the patient has visual disturbances while receiving HCQ, then an ophthalmologic evaluation will be done at that time. If the ophthalmologist recommends discontinuation of HCQ due to eye toxicity, then the patient will be taken off study for toxicity.

Patients receiving RGF are not required to have baseline or follow- up eye exams, unless there is crossover to the VOR/HCQ arm. If patient moves onto VOR/HCQ crossover arm, eye exam is as stated above (patient is 70 year or older or has baseline ophthalmologic).

∞ At baseline, archival tissue from diagnosis, but if not available, we need documentation of mCRC. Pre-cycle 2 tumor biopsy is optional. Follow instructions in **section 5.8.** ¶ Baseline should be done within 14 days of starting Cycle 1. Pre-cycle 2 and Off Treatment blood draws can occur +/- 3 days. Blood samples will be collected in five tubes: Two - 10-ml EDTA tubes for plasma, and Three - 8 mL Vacutainer CPT tubes for PBMCs. Follow instructions in **section 5.8.**

% NCI-CTCAE v4.0 will be used to document adverse events

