7.0 Data Collection

Data will be entered into Case Report Forms (CRF), which are currently in paper form.

For each patient on study, the following will be documented:

- Lab values: CBC, CMP, CEA, PTT/INR (when collected)
- PFS-1: measured from the start of the first treatment the patient is randomized to until the date the criteria for progression are met or the date the patient is taken off study for any reason, whichever is shorter).
- OS: measured from the start of treatment on trial until the death of the patient (date of death)
- PFS-2: measured from the start of the crossover treatment (Optional, second regimen) until the date the criteria for progression are met or the date the patient is taken off study for any reason, whichever is shorter.
- Response: measured as best response at any given time: complete response (CR) or partial response (PR), as defined by Response Evaluation Criteria in Solid Tumors (RECIST 1.1) Committee (73). (See Appendix 13.1 for definitions of response).
- Adverse events: the number and grade 1-5 of all adverse events will be documented according to the National Cancer Institute Common Terminology Criteria for Adverse Events (NCI-CTCAE) v4.0; measured at baseline, each cycle, and at off study date.

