- OS: The analyses of median OS will be performed in the intent-to-treat population. OS will be illustrated with Kaplan-Meier plots, the estimate of median OS with its 95% confidence interval. Treatment groups will be contrasted with regard to the response rate with a logistic regression model adjusted for age, sex, race and the baseline tumor K-RAS status (mutated, wild type); the odds ratio, its 95% confidence interval, and the p-value for testing the null hypothesis that the log odds ratio is zero will be presented. If the logistic model fails due to small cell counts then treatments will be contrasted with regard to response using Fisher's Exact Test.
- mPFS-2: The analyses of median PFS-2 will be performed in the crossover population. Crossover to the other arm will be allowed, but OPTIONAL, and will be determined by the treating physician for the patient's best interest. mPFS-2 will be illustrated with KaplanMeier plots, the estimate of median PFS-2 with its 95% confidence interval. Treatment groups will be contrasted with regard to the response rate with a logistic regression model adjusted for age, sex, race and the baseline tumor K-RAS status (mutated, wild type); the odds ratio, its 95% confidence interval, and the p-value for testing the null hypothesis that the log odds ratio is zero will be presented. If the logistic model fails due to small cell counts then treatments will be contrasted with regard to response using Fisher's Exact Test.
- Response rates: Response rates will be measured as the proportion of patients with the best response, complete response (CR) or partial response (PR), as defined by RECIST 1.1 Criteria and a 95% confidence interval. (See Appendix 13.2 for RECIST 1.1 criteria)
- Adverse events: All adverse events will be listed by type and grade. All adverse events will be listed by treatment group, level of seriousness (serious, not serious). Treatments will be contrasted with regard to each adverse event with Fisher's Exact Test.

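### PFS-1 and OS are timed from first dose, while only regorafenib is ordered from a specialty pharmacy after randomisation: unequal waits would bias PFS-1 by an unknown amount in an unknown direction, and never-dosed patients have no OS start date

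*Combined protocol and SAP*

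**What the plan says.** Section 5.7 gives the primary endpoint as "PFS-1: measured from the start of the first treatment the patient is randomized to until the date the criteria for progression are met", ending there "or the date the patient is taken off study for any reason, whichever is shorter". The secondary endpoint is "OS: measured from the start of treatment on trial until the death of the patient". The Synopsis and Section 7.0 use the same starting points.

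Under Randomization in Section 5.2, "The patient should start the treatment within 14 days of randomization" applies to both arms. For one arm only, "Upon randomization, regorafenib prescription will be sent to specialty pharmacy". If RGF arrives at 14 days or later, the Section 6.0 footnote says "then the patient will need a C1D1 clinical visit and labs: CBC, CMP, CEA, LDH"; Section 5.2 has a near-identical line. Neither lists a new scan. As context, the amendment summary (Section 13.0) explains these lines by the time RGF can take to reach the patient.

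Scans follow treatment: after two cycles, then at least every two cycles or 8 weeks (Section 5.3.1). Section 10.0 makes a patient who leaves the study before completing Cycle 1 not evaluable for efficacy. For OS, the same section states: "The analyses of median OS will be performed in the intent-to-treat population".

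**The concern.** Randomisation makes the arms comparable on the day of randomisation. An endpoint that starts later keeps that comparability only if the interval before it is alike in both arms. Here one arm has a supply step that the other is not described as having.

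PFS-1 is sensitive to this. The first scan, at 56 days, falls almost exactly at the assumed control median of 1.9 months, so a shift of days in tumour age at that scan changes how many patients are recorded as progressed. The direction depends on who is dosed. If everyone is eventually dosed, growth during the wait counts against RGF. If those who progress while waiting drop out, the RGF arm loses its early failures.

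The OS problem needs no assumption about delay. An intent-to-treat analysis includes every randomised patient, but the definition gives a never-dosed patient no day zero.

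**Working it through.** **1. The plan's own sample size.** Inputs from Section 10.0: medians 1.9 and 3.8 months (hazard ratio 0.5), 80% power, 36 months' accrual, 12 months' follow-up, 5% loss. Two-sided 0.05 is inferred from the interim and final boundaries.
- Freedman: events = (1.96 + 0.8416)² × [(1 + 0.5)/(1 − 0.5)]² = 7.849 × 9 = 70.6, so 71.
- Exponential event probabilities are 0.999 and 0.983, mean 0.991. 71/0.991 = 71.6, so 36 per group.
- 36/0.95 = 37.9, so 38 per group and 76 in total. The plan's figure is reproduced, and no step uses a time origin.

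**2. Why a wait matters at the first scan.** The control median is 1.9 × 30.44 = 57.8 days. With exponential progression, the share progressed by day t is 1 − 2^(−t/57.8).
- Dosed on the day of randomisation, scanned at day 56: 48.9%.
- Dosed 3 days later, scanned at day 59: 50.7%.
- Dosed 14 days later, scanned at day 70: 56.8%.

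**3. Simulated false wins under the current rules.** The waits are assumed, because the documents give none. Setting: 38 per arm; no treatment difference; median 57.8 days in both arms; baseline scan at randomisation; same risk while waiting as on drug; scans every 56 days from first dose; censoring at 365 days; log-rank test with critical value 1.96857 at the final look only. The log-rank test stands in for the planned adjusted proportional hazards model. Risk is equal across patients and VOR/HCQ does not wait unless stated. Figures are rounded; repeat runs differ by a few tenths of a point.

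| Assumed wait and handling | False VOR/HCQ wins % | False RGF wins % |
|---|---|---|
| No wait | 2.6 | 2.5 |
| All RGF wait 14 days, nobody lost | about 7.5 | 0.7 |
| RGF waits uniform 0–14 days, nobody lost | about 4.6 | 1.3 |
| As above, VOR/HCQ also waits 0–7 days | about 3.5 | 2 |
| VOR/HCQ waits 14 days, RGF 7, nobody lost | 1.4 | 4.7 |
| All RGF wait 14 days, half of wait-period progressors dropped | 4.8 | 1.3 |
| All RGF wait 14 days, all such patients dropped | 2.7 | 2.7 |
| As above, patients differ in risk (gamma frailty variance 1.0) | 0.9 | 6.3 |

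With a 14-day wait for all, the number who could be dropped is 38 × (1 − 2^(−14/57.8)) = 38 × 15.5% = 5.9 RGF patients.

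**4. Candidate repairs, all RGF waiting 14 days.**

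| Repair | False VOR/HCQ wins % | False RGF wins % |
|---|---|---|
| PFS-1 clock from randomisation, scans still from first dose | near 0 | about 27 |
| Clock and scans from randomisation, all analysed, untreated risk equal to on-drug risk | 2.6 | 2.5 |
| Same, untreated risk 1.5 times on-drug risk | about 4.6 | 1.5 |
| Same, untreated risk 2 times on-drug risk | about 7.0 | 0.7 |

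The first row fails because every RGF progression would be dated 14 days later than the matching VOR/HCQ scan.

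**5. OS.** The population is all randomised patients and the origin is start of treatment. For a patient never treated, the second does not exist. For scale only, at the cited RGF median of 6.4 months (194.8 days), 1 − 2^(−14/194.8) = 4.9% would die within 14 days. That is about 1.8 of 38 if every RGF patient waited that long.

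**The case against.** The strongest reply is that no delay has been shown. The 14-day target covers both arms. VOR/HCQ can wait too, since patients allocated to it who are 70 or older, or who have eye pathology, need a baseline eye examination. A 14-day wait for every RGF patient and none for VOR/HCQ is an extreme case. This stands, and it is why the point is conditional. The target is worded as advice, however, and the next lines provide for 14 days or more.

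A reader might infer that PFS-1 is biased towards VOR/HCQ, or that no PFS-1 result could be told apart from supply delay. The documents support neither. The table runs from no bias to bias in either direction. With nobody lost, a two-week RGF wait gives a null hazard ratio of about 0.84, against a design value of 0.5.

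A reader might also infer that the conflicting baseline-scan limits decide the sign. They do conflict: up to 6 weeks before enrolment (Section 4.0), within 6 weeks of treatment (5.3), Day −36 to −1 (6.0), and at most 4 weeks before treatment (12.1). But with scans 0 to 42 days old at randomisation, as Section 4.0 allows, the 42-, 36- and 28-day limits all give about 2% and 3.5%. The conflict needs reconciling but does not settle the direction.

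Nor does the absence of the randomisation date from the Section 7.0 list show that it will not be recorded. That list also omits arm, age and KRAS status, so it is plainly not exhaustive.

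Finally, Section 10.0 plans only Kaplan-Meier plots and medians for OS, with no test between arms. The OS point is a gap in the definition, not a demonstrated error rate.

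**Conclusion.** The concern holds as a design weakness that should be fixed. Two parts are certain from the text: both clocks start at a post-randomisation event with an arm-specific supply step, and the OS definition does not fit its intent-to-treat population. The size and direction of any PFS-1 bias are unknown. Under assumed waits of up to 14 days, equal risk and nobody lost, false VOR/HCQ wins rise from a nominal 2.5% to between about 3.5% and 7.5%. Dropping patients who progress while waiting can remove or reverse this. Confidence is high for the definitions and moderate for the practical importance, which depends on waits that the documents do not report.

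**What to change.** 1. Measure OS from randomisation in all randomised patients. This stands on its own.
2. Measure PFS-1 from randomisation and, in the same change, schedule tumour scans in calendar weeks from randomisation in both arms. The two must move together.
3. Make all randomised patients the primary PFS-1 population. Keep the Cycle 1 rule and PFS from first dose as sensitivity analyses. The off-study clause must then say how a never-dosed patient is handled.
4. Reconcile the baseline-scan statements into one window applied identically in both arms; its length is for the sponsor to choose.
5. Report time from randomisation to first dose by arm.

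The cost is wording in the Synopsis and Sections 4.0, 5.2, 5.3, 5.7, 6.0, 7.0, 10.0 and 12.1, plus scans for a few never-dosed patients. The 36/38/76 sample size is unchanged.

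The package does not guarantee nominal error. Delayed patients will have had less drug at the first scan, so some bias against the delayed arm remains if untreated risk is higher (last two rows of the second table). Scans will not fall exactly at cycle ends, and never-dosed patients may miss them.
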